8 STUDY SELECTION CRITERIA

8.1 INCLUSION CRITERIA

For inclusion in this study, subjects must meet all the following criteria (only one eye of each subject is eligible, and all ocular criteria apply to the study eye only unless otherwise indicated):

1. Male or female subjects, 22 years or older
2. Visually significant cataract
3. Diagnosed with mild to moderate open angle glaucoma (e.g. primary open angle glaucoma, pigmentary glaucoma, pseudoexfoliative glaucoma) as documented in subjects' medical record per ICD-10 guidelines
4. At screening, a medicated IOP \leq 33 mmHg and on 1-4 IOP-lowering medications with a stable medication regimen for two months prior to screening visit²⁸
5. At baseline, unmedicated diurnal IOP 21-36 mmHg and IOP at least 3 mmHg higher than screening IOP
6. Scheduled for cataract extraction followed by ab-interno transluminal viscoelastic delivery and trabeculotomy using the OMNI Surgical System
7. Shaffer grade of \geq III in all four quadrants
8. Potential of good best corrected visual acuity post cataract extraction, in the investigator's judgment
9. Able and willing to comply with the protocol, including all follow-up visits
10. Understands and signs the informed consent.

8.2 EXCLUSION CRITERIA

A subject who meets any of the criteria listed below (in the study eye, unless otherwise indicated) will be excluded from the study:

(All criteria apply to the study eye; both eyes of a single subject need not be eligible):

1. Any of the following prior treatments for glaucoma:

²⁸ For combination IOP-lowering medications that consist of two or more IOP-lowering drugs, each IOP-lowering drug component counts as a separate medication.

- Laser trabeculoplasty ≤3 months prior to baseline
- Implanted with iStent, Cypass, Xen, Express, glaucoma draining device/valve, or Hydrus Device
- Prior canaloplasty, goniotomy, trabeculotomy, trabeculectomy, ECP or CPC

2. Normal tension glaucoma
3. Acute angle closure, traumatic, congenital, malignant, uveitic or neovascular glaucoma
4. Severe glaucoma as documented in subjects' medical record per ICD-10 guidelines
5. Use of oral hypotensive medication treatment for glaucoma
6. In the investigator's judgement, predisposed to significant risk because of washout of ocular hypotensive medications.
7. Ocular pathology or medical condition which, in the investigator's judgment, would either place the subject at increased risk of complications, contraindicate surgery, place the subject at risk of significant vision loss during the study period (e.g., wet AMD, corneal edema, Fuch's dystrophy, etc.), or interfere with compliance to elements of the study protocol (e.g., returning to investigator's office for follow-up visits)
8. Participation (≤ 30 days prior to baseline) in an interventional trial which could have a potential effect on the study outcome, as determined by the study investigator.
9. Women of childbearing potential if they are currently pregnant or intend to become pregnant during the study period; are breast-feeding; or are not in agreement to use adequate birth control methods to prevent pregnancy throughout the study

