9 STUDY PROCEDURES

9.1 STUDY SCHEDULE

Table 1: Study Visit Schedule

Note: The fellow eye should be followed per the PI's usual practice based on the ocular health of the fellow eye.

PROCEDURE	SCREENING (DAY -45 TO -6)	BASELINE (DAY -7 TO 0)	SURGERY (DAY 0)	1 DAY (DAY 1)	1 Wk (DAY 5-9)	1 M (DAY 21-35)	3 M (DAY 70-98)	6 M (DAY 150-210)	12 M (DAY 330-420)	12 M WASHOUT ²⁹ (DAY 330-420)
Informed Consent	X									
Demographics	X									
Medical & Ocular History	X	X								
Medication Log	X	X	X	X	X	X	X	X	X	X
BCVA (ETDRS), with manifest refraction	X	X			X	X	X	X	X	
Visual Field (Humphrey 24-2 SITA)	X									X
IOP (Goldmann)	X			X	X	X	X	X	X ³⁰	
Unmedicated diurnal IOP (Goldmann)		X							X ³¹	X
Slit Lamp Exam	X	X		X	X	X	X	X	X	
Gonioscopy	X				X	X	X	X	X	
Dilated Fundus Exam/C:D Ratio	X								X	
Eligibility Assessment	X	X								
Cataract Extraction + ab-interno transluminal viscoelastic delivery and trabeculotomy			X							
AE Assessment	X	X	X	X	X	X	X	X	X	X

²⁹ The 12 month washout visit is only required for subjects who are taking hypotensive medications at the 12 month visit.

³⁰ This is only required for subjects who are taking hypotensive medications at the 12 month visit.

³¹ If subject is not on any hypotensive medications, a diurnal IOP measurement should be obtained at the 12 month visit as unmedicated IOP.

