9.5 WASHOUT OF HYPOTENSIVE MEDICATIONS

Subjects who meet all screening eligibility criteria will be instructed to discontinue their ocular hypotensive medication regimen in the study eye only, and to return for a Baseline visit after completing the appropriate washout period. Glaucoma medication discontinuation can be staged (for patients on multiple medications) so that the pressure increase duration is minimized to the greatest possible extent during the washout period. For example, if a patient is on a prostaglandin (PGA) and a Carbonic Anhydrase Inhibitor (CAI), the PGA could be discontinued 4 weeks prior to the Baseline visit but the allowed to continue until 5 days before Baseline.

If the study subject fails to remember to not use ocular hypotensive medication for the study eye per the required washout period, they can be re instructed to washout and return for the Baseline or 12-month washout IOP visit as long as it falls within the specified visit window.

The minimum wash-out periods are specified in Table 2 below. Note: The maximum washout period is 6 weeks. Therefore, if the study procedure cannot be scheduled within one week of the end of the washout period, the subject should be restarted on glaucoma medication until the Day 0 visit (but after the washed-out diurnal IOP has been obtained).

Table 2: Ocular Hypotensive Medication Washout Periods

Brand Name/Chemical Name	Minimum washout period
Carbonic Anhydrase Inhibitors	
Diamox® (Acetazolamide) – oral Rx	5 days
Neptazane® (Methazolamide) – oral Rx	5 days
Azopt® (Brinzolamide)	5 days
Trusopt® (Dorzolamide Hydrochloride)	5 days
Muscarinic Agonists	
Salagen, Pilocar (Pilocarpine)	5 days
Alpha Adrenergic Agonist	
Alphagan® (Brimonidine)	14 days
Iopidine® (Apraclonidine Hydrochloride)	14 days
Beta Blockers	
Betagan® (Levobunolol Hydrochloride)	28 days
Betoptic® (Betaxolol Hydrochloride)	28 days
OptiPranolol® (Metipranolol)	28 days
Timoptic/Betimol® (Timolol Maleate)	28 days
Prostaglandin Analogs	
Lumigan® (Bimatoprost)	28 days
Travatan® (Travoprost)	28 days
Xalatan® (Latanoprost)	28 days
Zioptan® (Tafluprost)	28 days
Vyzulta® (Latanoprostene Bunod)	28 days
Rho Kinase Inhibitor	
Rhopressa® (Netarsudil)	28 days
Combined Medications	
Combigan® (Brimonidine Tartrate/Timolol Maleate)	28 days
Cosopt® (Dorzolamide Hydrochloride/ Timolol Maleate)	28 days
Simbrinza® (Brinzolamide/Brimonidine Tartrate)	28 days
Other	Contact Sponsor

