9.10 WITHDRAWAL AND DISCONTINUATION

All subjects have the right to withdraw at any point during the treatment without prejudice. The investigator can discontinue any subject at any time if continued participation in the study would result in harm to the subject. All efforts should be made by the investigator to retain the subject in the study. If a subject withdraws prematurely from the study, a genuine effort must be made to determine the reason(s) the subject discontinued the study. The reason must be recorded in the subject's file and on the Study Exit Form.

If a subject withdraws from the study post-baseline but prior to surgery, then that subject may be replaced in the study by a newly enrolled subject.

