11 STATISTICAL CONSIDERATIONS

11.1 HYPOTHESES AND SAMPLE SIZE CALCULATION

11.1.1 SAMPLE SIZE FOR THE PRIMARY EFFECTIVENESS ENDPOINTS

First Primary Effectiveness Endpoint

The first primary effectiveness endpoint is the reduction in the unmedicated diurnal IOP from baseline to 12 months postoperatively. The study objective is to show that the mean unmedicated diurnal IOP reduction of the study treatment (i.e. ab-interno transluminal viscoelastic delivery and trabeculotomy performed with OMNI system performed after uneventful cataract extraction) is superior to that of the cataract extraction alone. Based on recent approved MIGS studies, the mean \pm SD unmedicated diurnal IOP reduction at 12 months for the cataract extraction alone is 6.7 mmHg \pm 3.6 mmHg (N = 118) for Glaukos P170043 and 6.3 mmHg \pm 4.0 mmHg (N = 187) for Ivantis P160024. Therefore, the mean \pm SD unmedicated diurnal IOP reduction at 12 months for the cataract extraction alone is estimated as 6.5 mmHg \pm 3.8 mmHg.

The corresponding statistical hypotheses are as follows:

$H_0: \mu_{OMNI} \leq 6.5$ mmHg and $H_a: \mu_{OMNI} > 6.5$ mmHg, where μ_{OMNI} is the mean unmedicated diurnal IOP reduction at 12 months for the OMNI Surgical System in combination with Cataract Extraction.

Based on a one-sample t-test with a one-sided significance level of 0.025 (or two-sided 0.05), a sample size of 116 eyes at 12 months provides a statistical power of 80% at a true μ_{OMNI} of 7.5 mmHg.

Second Primary Effectiveness Endpoint

The second primary effectiveness endpoint is the reduction in the number of IOP-lowering medications from screening to 12 months (before medications washed out if applicable) postoperatively.

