11.2 ANALYSIS POPULATIONS

The intent-to-treat (ITT) analysis population includes all subjects who are enrolled and treated, regardless of whether or not they have a protocol deviation. Due to the eligibility revision in May of 2019 on requiring at least one ocular hypotensive medication, the modified ITT (mITT) population includes all ITT except for the treated eyes that were not on any ocular hypotensive medication at the screening visit. The per-protocol analysis population (PP) is a subset of mITT, which includes all subjects who have taken at least one ocular hypotensive medication at screening and have uneventful cataract extraction followed by ab-interno transluminal viscoelastic delivery and trabeculotomy, 12 month IOP and medication data, and have no clinically significant protocol deviations. It should be noted that the mITT subjects with an uneventful study procedure but with SSIs before the 12-month visit will be included in the PP population even if they do not have the 12-month IOP and medication data. The primary analyses on the primary and secondary endpoint analyses will be carried out on the per-protocol population.

The safety data will be summarized based on the ITT population. The primary and secondary endpoint analyses will also be performed on the mITT population.

The data will be listed separately for the enrolled subjects that are not treated with OMNI and treated subjects that do not have ocular hypotensive medications at the screening.

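### An eye on drops at 12 months that is not washed out and has no SSI leaves the PP IOP co-primary and both PP secondaries, and mITT can fill its gap with an on-drops IOP

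*Combined protocol and SAP*

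**What the plan says.** Washout risk is named once, as an entry exclusion: 8.2 criterion 6 bars a patient whom the investigator judges "predisposed to significant risk because of washout of ocular hypotensive medications". There is no 12-month counterpart.

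The first co-primary and both secondaries use unmedicated diurnal IOP at 12 months (7.1). For eyes still on drops, 9.1 footnote 29 states: "The 12 month washout visit is only required for subjects who are taking hypotensive medications at the 12 month visit". The medicated Goldmann reading at the 12-month visit is kept for the same eyes by footnote 30: "This is only required for subjects who are taking hypotensive medications at the 12 month visit". Both visits share the window Day 330-420. Section 9.5 sets minimum washouts of 28 days for beta blockers, prostaglandins, netarsudil and the listed combinations, and adds: "The maximum washout period is 6 weeks". A patient who forgets to stop drops may repeat the washout within the window.

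The drug-count co-primary runs "from screening to 12 months (before medications washed out if applicable) postoperatively" (11.1.1), so it does not need the washout.

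PP is the primary analysis set for the primary and secondary endpoints. It requires "12 month IOP and medication data, and have no clinically significant protocol deviations" (11.2). The one exception is for eyes with an uneventful procedure and an SSI: "SSIs before the 12-month visit will be included in the PP population even if they do not have the 12-month IOP and medication data". Section 11.4.1 gives SSI eyes their last data before the SSI, and 11.4.2 makes them non-responders when the 12-month response is missing.

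For missing 12-month data without an SSI, 11.4.1 lists four optional imputations, for mITT only: within-eye worst, worst during the study, mean during the study, and last observation. Section 11.4.2 derives the mITT responder status from the imputed values.

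**The concern.** Section 9.9 discourages drops after surgery unless there is a medical need. An eye on drops at 12 months is therefore likely to have a below-average unmedicated result, and if it is not washed out that result is never measured. In PP the eye is simply absent from the tests that need the measurement. An SSI eye, the other kind of poor outcome, stays in and counts.

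This is a single-arm comparison with fixed goals of 6.5 mmHg, 73% and 55%, so no control arm shares the loss. Removing poor results raises the PP mean and responder rates directly against those goals. The mITT analysis should be the safeguard, but its imputation is optional and not limited to off-drops readings. Under last observation, the value carried forward can be the on-drops 12-month IOP itself, which can then make the eye a responder on an endpoint defined as unmedicated.

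**Working it through.** **1. Can the case arise?** Yes, and not only for safety. A 28-day washout that ends by Day 420 must begin by Day 420 − 28 = Day 392. A 12-month visit after Day 392 is in window but leaves no in-window washout for those drug classes. Refusal is another route.

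**2. What happens to the eye?**

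| Analysis | Eye with SSI | On drops, no SSI, not washed out |
|---|---|---|
| PP, IOP co-primary | kept, last pre-SSI value | no unmedicated value, no imputation: omitted |
| PP, both secondaries | non-responder if response missing | omitted |
| PP, drug count | kept | kept if the medicated reading satisfies the 12-month IOP requirement and the missed washout is not ruled a clinically significant deviation; otherwise omitted |
| mITT, IOP and secondaries | as above | optional imputation: mean or last observation can be on-drops; within-eye worst may be on- or off-drops; worst during the study is conservative if read across eyes |

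**3. The plan's own figure.** One-sample t-test, one-sided 0.025, difference 7.5 − 6.5 = 1.0 mmHg, SD 3.8 (11.1.1). The noncentral t gives power 0.799 at n = 115 and 0.803 at n = 116. The stated 116 reproduces.

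**4. Effect of PP omission on the IOP co-primary.** Assumptions, since the documents give neither figure: k = 2, 4 or 6 omitted eyes beside 116 analysed, with true mean reduction r = 0, 2 or 4 mmHg.

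- Overstated mean when the 116 average 7.5: 7.5 − (116 × 7.5 + k × r)/(116 + k).
- Error when the all-eye mean is exactly 6.5: the PP mean is (6.5 × (116 + k) − k × r)/116, put into the noncentral t with 115 df and SD 3.8. For example, k = 6 and r = 0 gives 6.5 × 122/116 = 6.836 and an error of 15.5%.

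| r (mmHg) | Overstated mean, k = 2 / 4 / 6 (mmHg) | One-sided error, k = 2 / 4 / 6 |
|---|---|---|
| 0 | 0.13 / 0.25 / 0.37 | 5.0% / 9.2% / 15.5% |
| 2 | 0.09 / 0.18 / 0.27 | 4.1% / 6.4% / 9.6% |
| 4 | 0.06 / 0.12 / 0.17 | 3.3% / 4.3% / 5.5% |

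**5. Secondaries.** Exact binomial, n = 116. The PP rate is (p0 × (116 + k) − h × k)/116, where h is the share of omitted eyes that would have responded.

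| Goal p0 | Critical count, size | h = 0, k = 2 / 4 / 6 | h = 0.5, k = 2 / 4 / 6 |
|---|---|---|---|
| 0.73 | 95, 1.7% | 3.4% / 6.5% / 11.4% | 2.2% / 2.7% / 3.3% |
| 0.55 | 75, 2.2% | 3.5% / 5.5% / 8.1% | 2.3% / 2.4% / 2.5% |

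**6. mITT filled with on-drops readings.** If drops lower IOP by d = 1 to 3 mmHg (assumed), the mean is overstated by d × k/(116 + k): from 1 × 2/118 = 0.02 to 3 × 6/122 = 0.15 mmHg. A responder rate is overstated by at most k/(116 + k) = 1.7, 3.3 or 4.9 percentage points.

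**The case against.** The case on the other side has real weight.

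- **Record-keeping.** A reader might infer that eyes not washed out would go unrecorded. The documents say otherwise. The visit is required, so missing it is a deviation. Section 14 requires a deviation form, 17.2.3 the dates and reasons, and 17.2.4 a report to the sponsor. A withdrawal reason goes on the Study Exit Form (9.10).
- **Discretion to waive washout.** A reader might also infer that the investigator may spare an eye the washout and keep it in the study. Section 9.10 says only: "The investigator can discontinue any subject at any time if continued participation in the study would result in harm to the subject". That is discontinuation, not a waiver.
- **Exclusion 6.** This is an entry criterion and not defective. It works against the scenario, because eyes judged at risk from washout are excluded and eligible eyes completed a washout before surgery. Nothing in the documents suggests that missed washouts will be common.
- **An existing rule.** Section 11.4.1 does address missing 12-month data without an SSI, and mITT analyses are promised alongside PP. Omitting eyes without endpoint data is what this PP definition does to any non-SSI eye.
- **Gatekeeping.** The secondaries are tested formally only if both primaries succeed, and the second only if the first succeeds (11.1.2). Their error rates above are for each test taken alone.

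What survives is narrower. For these eyes the missing value is linked to continued need for drops, the parallel SSI case is handled and this one is not, and the mITT rules do not exclude on-drops readings.

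**Conclusion.** The point holds and should be fixed. As written, an eye on drops at 12 months with neither a washout IOP nor an SSI is lost to the PP IOP co-primary and both PP secondaries. In mITT it may be given an on-drops value.

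The direction probably favours the device. That rests on 9.9, which makes restarted drops a marker of poorer control.

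The size is not known. A reader might take the 15.5% as the trial's error rate, but it needs six omitted eyes with no benefit at all. With a 4 mmHg true reduction the range is 3.3-5.5%, and if half the omitted eyes would have responded the secondaries stay between 2.2% and 3.3%. The mITT effect on the mean is small, 0.02-0.15 mmHg under the assumed drop effect. The gap in the rules is certain; its numerical effect is illustrative.

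**What to change.** 1. In 11.4.1, state that no on-drops IOP may stand in for the unmedicated 12-month IOP. Use the last off-drops postoperative IOP before drops were restarted, or baseline IOP if there is none.
2. In 11.2, 11.4.1 and 11.4.2, keep every eye on drops at 12 months without a washout IOP in both PP and mITT, whatever the reason. Use its observed pre-washout drug count, apply rule 1 to the IOP test (which mirrors the SSI rule), and count it as a non-responder on both secondaries.
3. Add a sensitivity analysis giving these eyes their baseline IOP (zero reduction). Report their number and reasons from the existing deviation and exit forms.

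Zero reduction belongs in the sensitivity analysis because it scores these eyes more harshly than SSI eyes. As the main rule it could be costly: with an all-eye mean of 7.5 mmHg and a true reduction of 4 mmHg in these eyes, simulated power falls from 80% to about 74%, 67% or 59% for 2, 4 or 6 eyes.

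The cost is a few SAP sentences, with no new form field and no washout waiver. The downside is slightly less favourable results. For example, if 85% of 116 eyes respond (98.6), adding six non-responders gives 98.6/122 = 80.8%.

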9 STUDY PROCEDURES

9.1 STUDY SCHEDULE

Table 1: Study Visit Schedule

Note: The fellow eye should be followed per the PI's usual practice based on the ocular health of the fellow eye.

PROCEDURE	SCREENING (DAY -45 TO -6)	BASELINE (DAY -7 TO 0)	SURGERY (DAY 0)	1 DAY (DAY 1)	1 Wk (DAY 5-9)	1 M (DAY 21-35)	3 M (DAY 70-98)	6 M (DAY 150-210)	12 M (DAY 330-420)	12 M WASHOUT ²⁹ (DAY 330-420)
Informed Consent	X									
Demographics	X									
Medical & Ocular History	X	X								
Medication Log	X	X	X	X	X	X	X	X	X	X
BCVA (ETDRS), with manifest refraction	X	X			X	X	X	X	X	
Visual Field (Humphrey 24-2 SITA)	X									X
IOP (Goldmann)	X			X	X	X	X	X	X ³⁰	
Unmedicated diurnal IOP (Goldmann)		X							X ³¹	X
Slit Lamp Exam	X	X		X	X	X	X	X	X	
Gonioscopy	X				X	X	X	X	X	
Dilated Fundus Exam/C:D Ratio	X								X	
Eligibility Assessment	X	X								
Cataract Extraction + ab-interno transluminal viscoelastic delivery and trabeculotomy			X							
AE Assessment	X	X	X	X	X	X	X	X	X	X

²⁹ The 12 month washout visit is only required for subjects who are taking hypotensive medications at the 12 month visit.

³⁰ This is only required for subjects who are taking hypotensive medications at the 12 month visit.

³¹ If subject is not on any hypotensive medications, a diurnal IOP measurement should be obtained at the 12 month visit as unmedicated IOP.

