9.9 MANAGEMENT OF IOP AFTER SURGERY

This protocol recommends that no IOP-lowering medications should be administered to subjects after the surgery (0 meds on postop day 1) unless medically warranted. Investigators should use their clinical judgement in determining when and why IOP-lowering medications should be reintroduced and if a subject requires surgical re-intervention to manage IOP.

Re-introduction of hypotensive medications should follow the guidelines below:

- The same medication class(es) as used preoperatively should be re-introduced. Dependent on preoperative IOP medication use, the reintroduction/addition of IOP medications postoperatively should follow the order below:
 1. Prostaglandin Analogues
 2. Alpha Agonists
 3. Beta Blockers
 4. Rho Kinase Inhibitor
 5. Carbonic Anhydrase Inhibitors (CAIs)
- No more than one ocular hypotensive agent should be added at a single visit or within a 2-week period.

³² 180° trabeculotomy should be attempted in every eye enrolled in the study. There is a possibility that 180° trabeculotomy may not be possible in each case.

In the event of a steroid response (IOP increase), the usual guidelines requiring a reproducible increase in IOP should be followed; however, topical hypotensive medications should be discontinued once the topical steroid has been discontinued.

If a pressure rise is observed, a paracentesis may be performed as necessary. If a paracentesis is performed and there is no protocol-defined adverse event, the paracentesis will be documented in the subject's medical record, the applicable visit CRF and the Ocular Procedures log. If, however, the paracentesis is performed in conjunction with an AE, then the AE is recorded as such, and the paracentesis is also recorded on the AE CRF as a treatment for the protocol-defined AE (as well as the other CRFs mentioned above).

Medications which have been re-started by the investigator may be discontinued if the investigator's judgment is that the target intraocular pressure has been reached and the continued use of some or all of the therapy may not be required. Discontinuation of medications after re-introduction is recommended to be in the reverse order of re-introduction. The rationale for discontinuation will also be documented on the follow-up form by the investigator.

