is too far forward. If the semicircles cannot be made "too large," the instrument is too far from the eye.

11. The fluorescein rings should be approximately 0.25 to 0.3 mm in thickness, that is, one tenth the diameter of the flattened area. If the rings are too narrow, the subject should blink two or three times to replenish the fluorescein; additional fluorescein may be added if necessary. If the fluorescein rings are too wide, the subject should dry his eyes lightly with a tissue, and the front surface of the prism should be dried with lint-free material. An excessively wide fluorescein ring is less of a problem than a very narrow ring but can cause the intraocular pressure to be overestimated.
12. The fluorescein rings normally undergo a rhythmic movement in response to the cardiac cycle. The tension knob is rotated until the inner borders of the fluorescein rings touch each other at the midpoint of their pulsations. The intraocular pressure is the mean of these 2 readings.
13. Intraocular pressure is measured in the study eye twice. If the 2 readings differ by 2 mmHg or less the average is the IOP. If the 2 readings differ by > 2 mm Hg, a third reading is taken.
14. The reading obtained in grams is multiplied by 10 to give the intraocular pressure in millimeters of mercury. This value is recorded along with the date, time of day, list of ocular medications, and time of last instillation of ocular medication if IOP is measured on different days, an attempt should be made to standardize the time.

Errors in measurement can arise from a number of factors, including the following:

1. Inadequate fluorescein staining of the tear film causes an underestimation of intraocular pressure.
2. Elevating the eyes more than 15° above the horizontal causes an overestimation of intraocular pressure. Widening the lid fissure excessively causes an overestimation of intraocular pressure.
3. Repeated tonometry reduces intraocular pressure, causing an underestimation of the true level. This effect is greatest between the first and second readings, but the trend continues through a number of repetitions.
4. A scarred, irregular cornea distorts the fluorescein rings and makes it difficult to estimate intraocular pressure.

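### The 12-month IOP counts as unmedicated with no minimum time off drops, so eyes whose drops were stopped shortly before the visit can carry residual drug effect into the IOP co-primary and both secondary endpoints

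*Combined protocol and SAP*

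**What the plan says.** Two footnotes to Table 1 (section 9.1) decide how the 12-month unmedicated IOP is obtained. Footnote 31 reads: "If subject is not on any hypotensive medications, a diurnal IOP measurement should be obtained at the 12 month visit as unmedicated IOP". Footnote 29 reads: "The 12 month washout visit is only required for subjects who are taking hypotensive medications at the 12 month visit". Both turn on whether the subject is currently on drops. Neither mentions time since the last dose.

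Section 9.5 sets that time elsewhere: "The minimum wash-out periods are specified in Table 2 below". Table 2 gives 5 days for carbonic anhydrase inhibitors and pilocarpine, 14 for alpha agonists, and 28 for beta blockers, prostaglandins, netarsudil and the listed combinations. Section 9.5 applies washout to two readings only. Subjects who forget to stay off drops may be told again, and "they can be re instructed to washout and return for the Baseline or 12-month washout IOP visit". The ordinary 12-month visit is not named.

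Section 9.9 governs stopping during follow-up: "Medications which have been re-started by the investigator may be discontinued if the investigator's judgment is that the target intraocular pressure has been reached" and continued therapy may not be needed. The rationale must be documented. No latest stop date before month 12 is given.

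Section 20.5 has each IOP value recorded with the "list of ocular medications, and time of last instillation of ocular medication". No rule in section 11 uses that item.

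**The concern.** Baseline IOP is measured after a class-specific washout, but the 12-month IOP need not be. By the protocol's own standard this is uneven. An eye still on a prostaglandin at month 12 must be off it for at least 28 days before its reading counts. An eye that stopped the same drug a week earlier is read at once and recorded as unmedicated.

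Residual drug effect lowers the 12-month IOP. That raises the measured reduction and helps an eye reach the 20% response. It nearly always helps the 6 to 18 mmHg response too, the exception being an eye pushed below 6 mmHg. The study has one arm and tests against fixed goals (6.5 mmHg, 73% and 55%), so no concurrent control carries the same error.

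**Working it through.** **Does another rule close the gap?**
- Section 11.1.2 describes the 12-month IOP as washed out where applicable, but Table 1 is what decides when washout applies.
- The per-protocol set in section 11.2 excludes clinically significant deviations. An eye handled as footnote 31 directs has no deviation.
- The time of last instillation is collected but not used.

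The gap stays open.

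**How wide is it?** The 6-month window ends on day 210 and the 12-month window opens on day 330. So 330 − 210 = 120 days or more pass without a scheduled visit. Drops stopped at the 6-month visit are far beyond 28 days by month 12, and an eye still on drops at month 12 goes to washout. Only eyes that re-started drops, then stopped them between scheduled visits within the Table 2 period before the 12-month visit (5 to 28 days by class), are caught.

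**The plan's own figures.** Inputs from section 11.1.1: goal 6.5 mmHg, true mean 7.5, SD 3.8, one-sided 0.025, power 80%. A one-sample t-test (noncentral t) needs n = 116, with power 0.8025, which agrees with the plan. Observed success at n = 116 needs a mean reduction of about 7.20 mmHg, that is 0.70 above the goal. Section 11.1.2 also reproduces by exact binomial: 105 eyes need 86 responders (alpha 0.0226, power 0.847), and 91 eyes need 60 (alpha 0.0223, power 0.832).

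**Bias in the IOP co-primary.** Let f be the share of analysed eyes caught and r their mean residual effect. Both are assumptions.
- Bias: b = f × r.
- SD of the mixture: s = √(3.8² + f(1 − f)r²).
- True type I error at μ = 6.5: the probability that a noncentral t on 115 df, with noncentrality b√116/s, exceeds its nominal one-sided 0.025 critical value.

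| f | r (mmHg) | b (mmHg) | s | Type I error |
|---|---|---|---|---|
| 2% | 1 | 0.02 × 1 = 0.02 | 3.803 | 0.0285 |
| 2% | 3 | 0.02 × 3 = 0.06 | 3.823 | 0.0365 |
| 5% | 1 | 0.05 × 1 = 0.05 | 3.806 | 0.0344 |
| 5% | 3 | 0.05 × 3 = 0.15 | 3.856 | 0.0612 |

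Of 116 eyes, 2% is about 2 and 5% about 6. These are errors of the IOP test taken alone; study success also needs the medication co-primary.

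**Secondary endpoints.** Let g be the share of all eyes turned from non-responder to responder. It cannot exceed f and will usually be smaller. Exact binomial at n = 116, critical counts 95 and 75:

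| g | 20% reduction (goal 73%) | 6 to 18 mmHg (goal 55%) |
|---|---|---|
| 0 | 0.017 | 0.022 |
| 1% | 0.030 | 0.036 |
| 2% | 0.050 | 0.057 |

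**The case against.** The best defence is that few eyes can be affected. Section 9.9 recommends no drops after surgery unless medically warranted. Stopping them is conditional on the investigator's judgement of target pressure and need, and changes are recorded on case report forms. With no scheduled visit in the preceding 120 days, a late stop needs a decision between visits. All of this stands: the route is narrow and the effect probably small. It does not remove the inconsistency, and the plan has no step that would show how many eyes took this route.

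A reader might also infer more than the documents support:

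- **That any eye skipping drops on the day qualifies.** The footnotes speak of being on, or taking, medication. An eye on a current regimen that missed a dose still belongs in washout. The gap concerns stopped regimens.
- **That the bias could match the planned effect.** With 20% of eyes and 3 to 6 mmHg, the product is 0.20 × 3 = 0.6 to 0.20 × 6 = 1.2 mmHg. The documents support neither input. The only scale for drug effect is the rise of at least 3 mmHg in inclusion criterion 5. That compares a baseline diurnal mean with a screening IOP before surgery, on the full regimen of 1 to 4 drugs, in eyes selected for the rise. It is a loose guide to what remains of a stopped, perhaps single, drug after surgery. The 6 mmHg has no source, and a full residual effect ignores decay after stopping.
- **That the medication co-primary is distorted by the same rule.** It is counted before any 12-month washout (section 11.1.1), so a late stop lowers the count whatever footnote 31 says. Correcting the footnotes leaves it unchanged.

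**Conclusion.** The point holds as a narrow inconsistency in the definition of a co-primary measurement. Footnotes 29 and 31 accept as unmedicated a reading that would not meet section 9.5 and Table 2 had it been taken at Baseline or at the 12-month washout visit. A site following the text exactly can produce such a reading, and the error favours success.

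Its size is unknown. At 2% to 5% of eyes and 1 to 3 mmHg, the bias is 0.02 to 0.15 mmHg against a planned margin of 1.0 mmHg, and type I error of the IOP test is about 0.029 to 0.061 against 0.025. These figures rest on the assumed f and r, SD 3.8 and 116 analysed eyes. If almost no eye stopped drops within the Table 2 period before month 12, the effect is negligible. It should be fixed, because the repair is cheap and the error runs one way, but the gap does not undermine the design or the sample size.

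**What to change.** **Definition.** Reconcile footnotes 29 and 31 with section 9.5 and Table 2, so that unmedicated has the same time-off-drug definition at baseline and at month 12. The content of that definition is for the sponsor and its clinical advisers. An eye that does not meet it at the 12-month visit has its diurnal IOP taken at the existing 12-month washout visit, within days 330 to 420.

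**Eyes already measured, or unable to finish within the window.** The two 12-month visits share one window. A drug with a 28-day minimum stopped after day 392 (420 − 28) cannot complete that period inside it. Flag such eyes from the Medication Log and the time of last instillation, and report their number. Keep them in the per-protocol primary analysis. Dropping their readings there would exclude eyes on a post-baseline criterion, because section 11.2 requires a 12-month IOP and section 11.4.1 offers imputation without secondary surgery only for the mITT set.

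**Sensitivity analysis.** Repeat the IOP co-primary and both secondary analyses with the flagged readings treated as missing and imputed by the within-eye worst-value rule of section 11.4.1, deriving responder status from the imputed IOP. State that the rule applies to flagged per-protocol eyes for this purpose. Because the 6-month value may itself have been taken on drug, list the flagged eyes with the readings used.

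**Cost.** Two footnotes, one derivation flag, one added sensitivity analysis, and a later diurnal visit for a few eyes. The 116 eyes at 12 months, and about 130 treated after 10% drop-out, stand.
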